	
Clinical photographs One bone-fill specimen per patient, harvested by trephine (placed in fixative for later histological analysis)
 
Surgeon's subjective observation of osseous fill quality (D-1-D-4) Randomized insertion of one, two-piece, dental implant per study site Immediate post-surgical intra-oral radiographs Prescriptions for post-surgery antibiotics and analgesics (prn) Antibacterial mouth wash and ice-packs dispensed Written and verbal home-care instructions
 
Post- Insertion Follow-up Implant surgical follow-up assessment and suture removal will be performed after two-weeks.
 
Implants Uncovered Mandibular implants will be uncovered after approximately 4 months; maxillary implants will be uncovered after approximately 6 months.
 
Implant Restoration Implants will be restored in the conventional manner with aesthetically pleasing cemented single crown restorations.
 
Longitudinal Follow-up Two annual follow-up evaluations will be completed at 12 months and 24 months after surgical implant placement. Each assessment will include:
 
Standardized intra-oral periapical dental radiographs Clinical photographs Measurement of clinical parameters Assessment of soft-tissue contours Assessment of overall aesthetics Assessment of implant/restoration interface Patient satisfaction survey

Population	
Eighty healthy adult patients (20 in each extraction group) of any ethnicity or gender whose treatment plan includes extraction of mandibular and/or maxillary pre-molars and/or maxillary anterior teeth and their replacement with root-form dental implants will be consecutively recruited for enrollment in the study.
 
Only treatment of non-adjacent sites will be included in the database. Each participant may have up to four non-adjacent sites selected for inclusion as study treatment sites.
 
Participants must be 19 years old or older with demonstrated ability to understand the proposed treatment recommendations and prognosis and be able to provide informed consent, in English, without the aid of ad hoc translation.

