3.0 STUDY POPULATION

3.1 Entrance Criteria

Eighty healthy adult patients (20 in each group) of any ethnicity or gender whose treatment plan includes extraction of maxillary anterior teeth and/or mandibular and/or maxillary pre-molars and their replacement with root-form dental implants will be consecutively recruited for enrollment in the study.

The study will include an initial minimum of six time-sensitive, clinic visits over eight consecutive weeks. Implants will be placed 8 weeks after extractions. Following implant placement, additional visits, necessary for health maintenance and implant restoration, will be scheduled at the study dentist's discretion. Participants will return for two follow-up visits at 12 and 24 months after implant placement.

Only treatment of non-adjacent sites will be included in the database. Each participant may have up to four non-adjacent sites selected for inclusion as study treatment sites.

Participants must be at least 19 years old with demonstrated ability to understand the proposed treatment recommendations and prognosis and be able to provide informed consent, in English, without the aid of ad-hoc translation from another language. Decisionally-impaired adults and/or minors, who cannot consent for themselves, will not be enrolled; women who are pregnant or lactating at the time of enrollment will be excluded. Women will be tested for current pregnancy status.

Prior to enrollment, prospective participants must agree to be available for the entire duration of the study, be compliant with needed study-related evaluations and demonstrate a willingness to comply with strict time-line requirements. Certain health and medication exclusions apply (table 1).

Table 1 Entrance Criteria

Inclusion	Exclusion
Existence of one or more non-adjacent teeth in the aesthetic zone that are scheduled for extraction	Pregnancy or nursing at the time of enrollment
Healthy enough to undergo the proposed therapy without compromise to their existing health status	Previous malignant neoplasm
Demonstrated willingness to comply fully with protocol time-line and procedural requirements	A known hypersensitivity to β -TCP or rhPDGF-BB
At least nineteen years old	A known hypersensitivity to Titanium metal
Able to read and understand written English without the aid of ad hoc interpretation	Any health condition that in the opinion of the clinical investigators may adversely affect bone healing

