4.2 Randomization

Participants will be stratified for smoking status and randomized to one of four extraction groups; three experimental groups utilizing three different bone grafting applications and a control group where extraction sockets will be allowed to heal naturally. A secondary randomization will be conducted to select one tooth site per subject to receive trephine sampling for histology evaluation. At the time of enrollment, each participant in groups 1-4 will be further randomized into one of two implant strata.

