5.4 Implant Selection

The diameter and length of the implant will be determined by the surgeon based on the tooth location, anatomy, and bone volume determined from the CT scan prior to placement. The collar surface will be determined by the randomization scheme.

Table 4 Implant characteristics

Implant Material:	Titanium Alloy - Ti-6Al-4V
Collar Surfaces:	Resorbable Blast Texturing (RBT) or Laser Thread Texturing (LTT)
Connection:	1.5mm deep internal hexagon
Diameters:	Ø3.5mm Ø4.0mm Ø5.0mm Ø6.0mm
Lengths:	9mm, 10.5mm, 12mm and 15mm

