12.4 Statistical Analysis

The general approach to statistical analysis of the study aims will be based on mixed-model analysis of variance (ANOVA). This approach will accommodate the inclusion of correlated observations due to study subjects potentially contributing measurements of more than one single tooth site to the analysis.

The sample distributions will be examined for each outcome variable. If these distributions depart substantially from normality, transformations of the data will be evaluated. If normality cannot be established by transformation, rank-based analyses will be used.

Subjects will be included as a random effect on the analyses that include multiple observations per subject. For analysis of histological data, only one tooth site per subject will be evaluated and the model will not include a random effect.

Smoking status will be included in all models in order to account for differences in response between smokers and non-smokers, and so that the analysis will correspond to the study's randomization strategy. Comparisons between smokers and non-smokers are not a primary interest in the study.

For aims in which interaction terms are of interest, significant interaction terms will be investigated using plots of least square means and separate post-hoc analyses for individual time points.

Hypothesis 1

Differences among the four groups will be evaluated by the overall F-test for the ANOVA. Pairwise comparisons among group means will be conducted using Tukey's test. Contrasts will be constructed to address each specific aim (SA).

SA-1: Compare alveolar ridge dimensions in grafted extraction sockets to that of sites healed without grafts after 8 weeks of post-extraction healing.

This SA will be addressed by comparing the combined mean of the three graft groups (FDBA/TCP, DDBA/TCP/PRP, FDBA/TCP/PDGF) with that of the CONTROL group by calculating a contrast and the corresponding F-test. Pairwise comparisons among means will be conducted using Tukey's test..

Hypothesis II

The addition of growth factors to bone grafting materials will enhance osseous and soft tissue healing.

SA-2: Assess the efficacy of bone grafting with and without enrichment with growth factors to preserve the volume of bone in extraction sockets.

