This SA will be addressed using mixed-model ANOVA to compare mean bone volume among the four groups. Post-hoc pairwise comparisons will use Tukey's test. The effect of growth factors enrichment will be addressed using contrasts and F-tests to compare the mean of Group-4 with those of each of the other groups. If there is not a significant difference among the group means of Groups 1-3, the combined mean of these three groups will be compared with that of Group-4.

SA-3: Compare soft tissue healing between groups at week-1, week-2, week-4 and after 8 weeks of healing.

The analysis of SA-3 will be mixed-model ANOVA including measurements of healing made at each time points. Time will be included in the model in order to account for unequal spacing of the observational times. The statistical test that will be of primary interest will be the F-test for Group by time interaction.

SA-4: Assess quantitative bone fill across groups after 8 weeks post-extraction healing.

Qualitative bone fill will be compared among four groups using mixed-model ANOVA and the 8 week measurement only. Post-hoc pairwise comparisons will use Tukey's test.

SA-5: Compare qualitative bone fill across groups after 8 weeks post-extraction healing.

Percent new bone, percent residual graft, and percent soft-tissue will be compared among the four groups using ANOVA. For this analysis, there will be a single measurement of each of the variables per participant, so correlated observations will not be an issue in the analysis. Post-hoc pairwise comparisons will use Tukey's test.

SA-6: Assess the relationship of osseous healing and implant stability at insertion across groups after 8 weeks post-extraction healing.

This SA will be addressed by including the implant stability measure as a predictor variable in the analysis of osseous healing. The statistical test that will be of primary interest for this analysis will be the two-factor interaction of stability and group.

Hypothesis III

Laser thread-textured (LTT) dental implant will preserve longitudinal peri-implant crestal bone more effectively than implants with Resorbable blast texturing (RBT).

SA-7: Assess the efficacy of LTT and RBT surface topographies when surgically implanted into extraction sockets.

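### The SA-1, SA-2 and SA-4 models pool maxillary anterior teeth with premolars of both jaws and have no tooth-position or socket-size term, which costs precision in comparisons that the plan already rates at 52% to 57% power

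*Combined protocol and SAP*

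**What the plan says.** The Synopsis (Population) admits patients due for "extraction of mandibular and/or maxillary pre-molars and/or maxillary anterior teeth", and section 3.1 repeats this. Section 3.1 adds: "Each participant may have up to four non-adjacent sites selected for inclusion as study treatment sites". Nothing limits a participant's sites to one tooth type or one jaw.

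Section 4.2 stratifies on one factor: "Participants will be stratified for smoking status and randomized to one of four extraction groups". Section 12.4 carries that factor into the analysis ("Smoking status will be included in all models in order to account for differences in response between smokers and non-smokers") and handles repeated sites through the participant: "Subjects will be included as a random effect on the analyses that include multiple observations per subject".

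The aims concerned are these:

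- **SA-1** compares ridge dimensions after 8 weeks, grafted against control. No baseline term is stated.
- **SA-2** is addressed "using mixed-model ANOVA to compare mean bone volume among the four groups". No baseline term is stated.
- **SA-4** compares bone fill and is expressly limited to the 8-week measurement.

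None of the three names tooth position, jaw or socket size. The only general allowance for further covariates is in the SA-7 Cox model, which belongs to the implant stage. Section 4.8 (item 4.8-1) has the mesio-distal and bucco-lingual socket distances recorded at extraction, but no model uses them.

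**The concern.** Ridge dimensions and bone volume are size measurements, and bone fill at a single time point can depend on size as well. They are pooled over sockets of different tooth classes. The protocol itself treats location as bearing on size: section 5.4 has the surgeon choose implant diameter and length "based on the tooth location, anatomy, and bone volume". Tooth position is known for every site before extraction and treatment cannot change it, so it is a natural adjustment variable.

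The participant random effect does not do this job. Treatment is assigned by participant, so differences between participants in tooth mix stay in the error for the group contrast. Differences between teeth in the same mouth stay in the residual.

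At stake is power that section 12.5 already puts at 57% (SA-1) and 52% (SA-2 and SA-4) for a medium effect.

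**Working it through.** **Inputs from section 12.5.** Two-sided test at the 5% level; difference 0.50 sd; effective sizes 25 (control) and 75 (grafted) for SA-1; 25 per group for the four-group ANOVA; ICC 0.50. Twenty participants per group are recruited (section 3.1).

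**Assumed.** R², the share of within-group site variance explained by the added terms, is not in the documents. It is taken as 5% to 40%.

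**Step 1: the plan's own figures.** For SA-1 the noncentrality is λ₀ = 0.50² × (25 × 75)/(25 + 75) = 0.25 × 18.75 = 4.69 on 98 df. Power is 57.3% (stated 57%). The difference detectable with 80% power is 0.653 sd (stated 0.65). For the four-group ANOVA with f = 0.25 and 25 per group, power is 51.8% (stated 52%). All three reproduce.

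**Step 2: explained variance split proportionally between and within participants.** The error sd becomes √(1 − R²), so λ = λ₀/(1 − R²), and f becomes 0.25/√(1 − R²). Two df are deducted for a three-level factor.

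| Assumed R² | λ, SA-1 | SA-1 power | ANOVA power (SA-2, SA-4) |
|---|---|---|---|
| 0 | 4.69 | 57% | 52% |
| 5% | 4.93 | 59% | 54% |
| 10% | 5.21 | 62% | 57% |
| 20% | 5.86 | 67% | 62% |
| 30% | 6.70 | 73% | 69% |
| 40% | 7.81 | 79% | 76% |

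SA-1 would need R² of about 0.41 to reach 80% power.

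**Step 3: explained variance entirely within participants.** Set the total variance to 1 with ICC 0.50. The variance of a participant's mean over m sites is 0.5 + 0.5/m before adjustment and 0.5 + (0.5 − R²)/m after. The residual ICC rises, so effective sample size falls and the gain is smaller. λ₀ is multiplied by the ratio of the two variances, which keeps the unadjusted power at the plan's 57%.

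- m = 1.5: before, 0.833. At R² = 10%, after = 0.767, ratio 1.087. At R² = 40%, after = 0.567, ratio 1.471.
- m = 2: before, 0.750. At R² = 10%, after = 0.700, ratio 1.071. At R² = 40%, after = 0.550, ratio 1.364.

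| Assumed R² | SA-1 power, m = 1.5 | SA-1 power, m = 2 |
|---|---|---|
| 10% | 61% | 60% |
| 20% | 65% | 63% |
| 30% | 69% | 67% |
| 40% | 74% | 71% |

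The choice of m follows section 12.5. Its 120 and 160 observations over 80 participants are 1.5 and 2 sites each, and its VIFs of 1.25 and 1.5 equal 1 + (m − 1) × 0.50.

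**Step 4: the cost if the terms explain nothing.** With R² = 0, SA-1 power is 57.30% unadjusted, 57.28% with 2 df deducted, and 57.26% with 4 df deducted (tooth position plus two socket dimensions). The loss is below 0.1 percentage point.

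**The case against.** The strongest reply is that nothing here is an error. Participants are randomised, the model matches the stratification factor by design, and chance imbalance in tooth mix is already reflected in the standard error. That stands. A reader might infer that the group comparisons are biased or invalid without a tooth term; the documents do not support that.

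A reader might also infer that SA-1 and SA-2 analyse raw 8-week values. Only SA-4 says so. Hypothesis I and SA-2 speak of preserving dimensions and volume, the Synopsis lists changes in osseous architecture over time, and section 8.1 has a CBCT after grafting and another at 8 weeks. If change within a site is what is analysed, part of the tooth-size variation cancels and the gain is smaller. What stands is that no change score or baseline term is stated for either aim.

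Extending the point to SA-5 is tempting, because its stated power is the lowest at 42%. But its outcomes are percentages from a 2 × 6 mm core (section 12.1), and socket size does not scale a percentage in a fixed-size core. The documents give no other reason why tooth position should matter there.

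Finally, a three-level factor is a coarse proxy: it puts maxillary incisors and canines in one level. The recorded socket dimensions address size more directly. That is accepted and shapes the fix.

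**Conclusion.** The point holds for SA-1, SA-2 and SA-4 as an avoidable loss of precision. Tooth classes are pooled, and no stated term takes up tooth position or socket size.

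The size of the benefit is unknown, because R² is an assumption throughout. For SA-1 at 0.50 sd, the gain over 57% runs from about 2 points (R² = 5%, proportional split) to about 22 points (R² = 40%, proportional split). If the explained variance lies wholly within participants, the range at R² of 10% to 40% is about 3 to 17 points. The upper figures should not be read as expected values. The case for the change does not depend on them, since the cost is negligible even if R² is zero.

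**What to change.** In section 12.4, prespecify tooth position (maxillary anterior, maxillary premolar, mandibular premolar) as a fixed effect in the SA-1, SA-2 and SA-4 models, alongside smoking and the participant random effect. Preferably add the mesio-distal and bucco-lingual socket dimensions from item 4.8-1 as covariates. The first CBCT is a less clean choice, because section 8.1 has it taken after grafting, when treatment may already affect it. Leave SA-5 as it is.

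The cost is a sentence or two in the plan, 2 df for tooth position and 1 for each socket dimension. It needs no new data and no further participants. Naming the terms before analysis also avoids a post hoc choice of covariates.

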Hypotheses	
Hypothesis I Bone grafted sites preserve alveolar ridge dimensions of extraction sockets more effectively than extraction sites that have healed without grafting.
 
Hypothesis II The addition of growth factors to bone grafting materials will enhance osseous and soft-tissue healing.
 
Hypothesis III Laser Thread Textured (LTT) dental implant will preserve longitudinal peri-implant crestal bone more effectively than implants with a Resorbable Blast Textured (RBT) surface.

Randomization	
Participants will be stratified for smoking status and randomized to one of four extraction protocol groups and one of two implant groups:
 
Extraction Groups:
 
 Group 1. Atraumatic extractions followed by saline irrigation and natural healing [Control] Group 2. Atraumatic extractions followed by Freeze-Dried Bone Allograft (FDBA) Tri-Calcium Phosphate (TCP) + collaplug Group 3. Atraumatic extractions followed by FDBA/TCP/Platelet-Rich Plasma (PRP) +collaplug Group 4. Atraumatic extractions followed by FDBA/TCP/Platelet-Derived Growth Factors (PDGF) + collaplug 
A secondary randomization will be conducted to select one tooth site per subject to receive trephine sampling for histology evaluation.
 
Implant Groups:
 
 Group-A. LTT collar surface topography Group-B. RBT collar surface topography

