This SA will be addressed using a survival analysis approach. The primary outcome measure will be presence of signs and symptoms of infection at the implant site, since implant failure is expected to be rare to non-existent. Frequencies of occurrence of infection will be tabulated for each implant type.

Cox proportional hazards regression will be used to evaluate the rates of infection for LTT and RBT implants, allowing for adjustment for potential confounding variables and covariates. A blocking variable representing the individual subject will be included in order to reflect multiple implants per study subject.

SA-8: Assess peri-implant soft tissue healing adjacent to LTT and RBT surfaced implants

The JEMPT index will be evaluated at the time of final restoration and at 12 and 24 months follow-up evaluations. Mixed model ANOVA will be used to compare changes over time between implant types. The statistical test that will be of primary interest is the implant type by time interaction.

SA-9: Assess changes in the longitudinal crestal bone levels across extraction groups and between implant groups at 12 and 24 months after surgical placement.

The analysis for the SA will be mixed-model ANOVA, accounting for multiple observations per subject. The statistical test that will be of primary interest is the F-test for surface type by time interaction.

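### Section 12.4 puts smoking in every model but names no smoking-by-time term; as a main effect only, smoking has almost no influence on the time-interaction tests that lead SA-3, SA-8 and SA-9, which lose precision if smokers change at a different rate.

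*Combined protocol and SAP*

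**What the plan says.** Section 12.4 sets one rule for smoking across all analyses: "Smoking status will be included in all models in order to account for differences in response between smokers and non-smokers". It gives a second reason, "so that the analysis will correspond to the study's randomization strategy". It does not say in what form smoking enters, and neither 12.4 nor the synopsis names a smoking-by-time term.

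Three aims are led by a test of change over time:

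- SA-3 (soft-tissue healing at weeks 1, 2, 4 and 8): "The statistical test that will be of primary interest will be the F-test for Group by time interaction".
- SA-8 (soft-tissue index at final restoration, 12 and 24 months): "The statistical test that will be of primary interest is the implant type by time interaction".
- SA-9 (crestal bone level): "The statistical test that will be of primary interest is the F-test for surface type by time interaction".

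On allocation, section 4.2 states "Participants will be stratified for smoking status and randomized to one of four extraction groups". For the implants it adds only that "each participant in groups 1-4 will be further randomized into one of two implant strata", without repeating the stratification. The synopsis covers both allocations in one sentence: participants are stratified for smoking and "randomized to one of four extraction protocol groups and one of two implant groups".

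Section 12.5 bases the SA-8 and SA-9 power on a t-test of changes, with the SD of change taken within implant group and no reduction for smoking.

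**The concern.** Smoking status is fixed within a participant. A smoking main effect shifts all of a participant's visits by the same amount, so it drops out of every difference between visits, as the subject random effect does. The interaction tests are built from those differences. Fitted as a main effect only, smoking therefore serves neither of its stated purposes in the tests that lead three aims.

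Power is at stake. If smokers heal or lose bone at a different rate, that variation stays in the error term although the design balanced it across arms. These aims have little power to spare: section 12.5 gives 70% at a medium effect for SA-8 and SA-9, and 52% for the ANOVA model that it also applies to SA-3. SA-9 is also the only analysis in 12.4 of the crestal-bone outcome in Hypothesis III.

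**Working it through.** **Inputs from section 12.5.** Two-sided 5% testing; difference of 0.50 sd; effective sample size 50 per implant group (given there for SA-7, used here for SA-8/SA-9); stated power 70% at 0.50 sd and 80% at 0.565 sd. **Assumed, because the documents give no figure:** smoker share p of 0.1 to 0.5, and a difference δ in mean change between smokers and non-smokers of 0, 0.5 or 1.0 within-stratum SDs.

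**1. The plan's figures reproduce.** A two-sample t-test with 50 per group gives 69.7% at 0.50 sd and 79.9% at 0.565 sd. A four-group ANOVA with 25 per group and f = 0.25 gives 51.8%, against the stated 52%.

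**2. A main effect cancels.** Write the outcome of participant i at visit t as group + time + group×time + β·smoker + subject effect + error. In the difference between two visits, both β·smoker and the subject effect disappear. Mixed models fitted to simulated data (80 participants, three visits, 30% smokers, δ = 1.0) show the same:

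| Data | No smoking term | Smoking main effect | Smoking and smoking×time |
|---|---|---|---|
| Complete, one site each | F 0.29384, SE 0.2150 | F 0.29384, SE 0.2150 | SE 0.2072 |
| Complete, 1–2 sites | F 2.361, SE 0.1922 | F 2.359, SE 0.1923 | SE 0.1856 |
| 1–2 sites, 15% missing | F 0.026, SE 0.1904 | F 0.020, SE 0.1903 | SE 0.1860 |

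(In the last row the SE is that of the first time contrast.)

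**3. Size of the loss for a two-point change.** Leaving smoking×time out multiplies the variance of change by v = 1 + p(1−p)δ², so the SE is too large by a factor √v. Taking the plan's sd as the total SD of change, the fix raises the detectable effect from 0.50 to 0.50√v within-stratum SDs. For example, p = 0.5 and δ = 1.0 give v = 1 + 0.25 = 1.25, √v = 1.118 and an effect of 0.559.

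| δ | p | v | SE too large by | Effect (sd) | Power with smoking×time |
|---|---|---|---|---|---|
| 0.5 | 0.1 | 1.0225 | 1.1% | 0.506 | 70.6% |
| 0.5 | 0.3 | 1.0525 | 2.6% | 0.513 | 71.9% |
| 0.5 | 0.5 | 1.0625 | 3.1% | 0.515 | 72.3% |
| 1.0 | 0.1 | 1.09 | 4.4% | 0.522 | 73.4% |
| 1.0 | 0.3 | 1.21 | 10.0% | 0.550 | 77.7% |
| 1.0 | 0.5 | 1.25 | 11.8% | 0.559 | 79.0% |

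At δ = 0, v = 1 and nothing changes. The step up from 70% slightly overstates the gain where allocation is stratified, because the estimate is then already more precise than its reported SE. On a normal approximation the main-effect-only test has Φ(0.54√v) power, which is about 71–73% at δ = 1.0.

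**4. Type I error.** Simulation with 20,000 runs, 100 participants and 30% smokers:

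| δ | Main effect only, stratified | With smoking×time, stratified | Main effect only, unstratified |
|---|---|---|---|
| 0 | 5.0% | 5.0% | 4.8% |
| 0.5 | 4.6% | 5.2% | 5.2% |
| 1.0 | 3.3% | 5.1% | 5.0% |

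The approximation 2Φ(−1.96√v) agrees: 4.4% at δ = 0.5 and 3.1% at δ = 1.0.

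**5. More than two visits.** Simulated F-tests with a linear smoker trend and stratified allocation give the following gains from adding smoking×time, the 1.0 sd figures being for smoker shares of roughly 0.3–0.5. For three visits and two implant types the gain is about 1 power point at δ = 0.5 and 5–6 at δ = 1.0. For SA-3 (four groups, four visits) it is about 1–2 and 7–8 points.

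**The case against.** The strongest reply is that the plan never says main effect only. A rule that smoking is in all models does not exclude smoking by time, and its purpose of allowing for different responses could even support it. That stands: the form is unstated, and main effect only is a reading. It is the natural one, because 12.4 names its other interactions where it wants them. If both readings are open, they give different F-tests for three aims and the plan does not choose between them.

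A reader might infer that these tests do have oversized error bars. The documents do not support this. It follows only if smoking affects the rate of change, and they give neither that difference nor the smoker share. The gain is small at 0.5 sd, and the largest figures need a full 1.0 sd together with many smokers.

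A reader might also infer that the SA-8 and SA-9 tests are certainly conservative. That needs implant allocation to be stratified by smoking. The synopsis reads that way, but section 4.2 does not repeat it. If allocation was unstratified, error rates are correct and only precision is lost.

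Nor is the smoking term useless. It works in the group and implant-type main effects, and in the post-hoc analyses at single time points that follow a significant interaction. Section 12.3 derives bone change from insertion; if SA-9 is run on that outcome, the main effect absorbs a smoker difference in average loss. The leading interaction is then the 12 versus 24 month contrast, from which smoking still cancels.

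**Conclusion.** The point holds as a modest and conditional loss of efficiency. If smoking is fitted as a main effect only, it has essentially no influence on the leading tests of SA-3, SA-8 and SA-9, so the rule does not make those tests correspond to the stratified design.

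The cost rests on an assumed smoker difference in change: slight at 0.5 sd, material at about 1.0 sd when smokers are not rare, and nil if smoking does not affect change. The power range for SA-8/SA-9 further assumes a two-point change with 50 effective observations per implant group. For SA-3 the stratification is explicit, so the conservative error rate applies whenever smoking affects change; for SA-8 and SA-9 it depends on the synopsis being right. The direction is benign: power may be lost, but there is no bias and no excess of false positives. This is a cheap improvement to the model and does not invalidate the analysis.

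**What to change.** In section 12.4 and the synopsis, state: *In models whose test of interest involves time (SA-3, SA-8, SA-9), smoking status and the smoking-by-time interaction will both be included.* Keep the smoking main effect alone for single-time-point models.

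The cost is one sentence and 1–3 error degrees of freedom (one per time contrast: up to three for the four visits of SA-3, two for the three of SA-8, one if SA-9 compares only 12 and 24 months). No new data are needed, because smoking is already the stratification factor.
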